In 2005, the UN Special Rapporteur on the Right to Health affirmed that human rights training is fundamental for providing health professionals (including mental health practitioners) with the knowledge and tools to protect and promote human rights in their work [169]. This vision has been strongly endorsed at the international level, and led to the development – still ongoing - of human rights training manuals and capacity-building courses targeting health professionals [43, 53]. A recent review of the literature [43] found that human rights curricula in health professional education use different approaches to increase providers knowledge on this topic, including lectures from academics and experts in the field, group work, individual case studies, journal clubs, and contacts with persons whose rights have been violated. These initiatives have been shown to increase providers' awareness of human rights and, when measured, to improve their attitudes towards marginalized groups [43, 54]. Furthermore, since the promulgation of the UN CRPD, there has been sustained interest over developing trainings or manuals aiming to educate health professionals about the rights of people with psychosocial disabilities, although, so far, most of the materials produced do not target specifically this group [144, 170].

- **Strategy 2 for the elimination of violations: To change mental health professionals' attitudes towards people with psychosocial disabilities and their role as right holders.**

There have been numerous initiatives aimed to challenge the negative attitudes of society towards people with psychosocial disabilities [55, 171, 172]. All these initiatives used distinct educational approaches (e.g., the teaching of skills, social contacts with persons with psychosocial disabilities, engagement in myth-busting) and were evaluated in studies using different designs. Interventions to address stigma among health professionals are uncommon. In a recent systematic review, Henderson et al. [55] examined the effect of anti-stigma programs targeting health professionals (including mental health providers), and identified only 16 studies (three were RCTs, one a previous systematic review, the others were cross-sectional and pre-post intervention studies with or without control) on this topic. Educational trainings delivered by an expert (usually a mental health professional) were the most common type of intervention examined by investigators. Other interventions used internet courses, video presentations, module booklets, or contact-based education projects to address providers' stigma towards people with psychosocial disabilities [55]. Overall, these initiatives were found to be somewhat effective in reducing providers' negative attitudes towards people with psychosocial disabilities.

However, a problem with the existing interventions is that they often do not follow a modern human rights framework (as the one promoted by the UN CRPD). Indeed, these interventions are mainly developed by health practitioners, and thus, they often reflect their perspective, even when this is in contradiction with the CRPD principles and the position of people with psychosocial disabilities. Instead, education on human rights and interventions to address negative attitudes should be based on the modern framework of the UN CRPD and reflect the perspective of people with psychosocial disabilities and their organizations. Another problem concerning the initiatives to address stigma is that they focus on changing mental health professionals' negative attitudes towards people with psychosocial disabilities in general. None of these interventions follows a human-rights based approach and focuses specifically on changing attitudes towards people with psychosocial disabilities' role as rights-holders, although this aspect is fundamental for their full participation in society. Additionally, only a few studies evaluating the impact of human rights training also focused on assessing their ability to change attitudes. However, we assume that improvements in attitudes are an important mediator in the relationship between human rights knowledge and a change in behaviors, our ultimate goal, and thus they should have been more carefully assessed. Even among the studies to address health professionals' stigma, only two [56, 57] assessed a change in behaviors. However, none of them assessed a change in behaviors related to substitute-decision making and coercion.

Another problem is that all the studies [43, 55, 150, 172] evaluating the efficacy of these different interventions present important limitations. Many were pre-post intervention studies, with or without a control group. There is no reason to believe that the observed improvements in knowledge and attitudes would have occurred as

a result of current secular trends, but this cannot be definitively excluded without a control group. Even when the control group was present, most of the studies were non-randomized, and thus we cannot exclude non-comparability between the intervention and the control group. In the few cases where a randomized controlled trial was carried out, the samples enrolled were too small to draw definitive conclusions on the efficacy of the initiatives, and no power calculations were provided. Response rates in many pre-post intervention studies were low, particularly in the post-intervention assessments. This may have caused selection biases. For instance, we could have had a scenario in which the training content was causing loss to follow up (e.g., because the sessions were too lengthy or not engaging) and personal characteristics of participants (e.g., strong endorsement of coercive practices in mental health) were common causes both of the loss to follow up (affecting it positively) and the change in knowledge and attitudes (affecting it negatively). In this case, the results of the studies would have been biased away from the null. Information bias was an issue in many studies since the changes in knowledge and attitudes were evaluated with questionnaires not tested for reliability and validity. No attempt to quantify the impact of these biases was made in any of these studies. Furthermore, only the short-term effect of these programs was usually evaluated (pre-post assessment), and thus, there are no data on more long-term gains. In the future, it would be critical to design methodologically robust studies, carefully conceived to avoid confounding, selection bias, and information bias issues, and with longer follow-ups to evaluate these programs.

2.5. Steps forward: justifying a randomized controlled trial to test the WHO QualityRights training, a new promising intervention

We have seen that many interventions have been implemented in the past to increase mental health professionals' knowledge about human rights and change their attitudes towards people with psychosocial disabilities. Unfortunately, we have also seen that such interventions aimed to achieve only one of these objectives at a time or did not follow a modern human rights framework, like the one promoted by the UN CRPD. Furthermore, none of these interventions assessed a change in health professionals' practices related to substitute-decision making and coercion.

Recently, the World Health Organization (WHO) has launched the QualityRights (QR) initiative [58], which aims to promote the human rights of people with psychosocial disabilities across the globe. As part of the QualityRights initiative, the WHO has developed the QualityRights training. This intervention is different from the ones implemented in the past because it applies the modern framework of the UN CRPD. The QualityRights training includes five modules [see Appendix 2] created to increase the knowledge about the rights of people with psychosocial disabilities and change the negative attitudes towards these persons and their role as rights holders. Furthermore, the training provides mental health providers with the skills necessary to advocate for a human rights-based approach in mental health and support people with psychosocial disabilities to advocate for their rights. This training can be delivered through an online platform and includes presentations, videos, interactive exercises, and forum discussions involving all participants. The discussions are moderated by a multidisciplinary team of coaches, including people with psychosocial disabilities, professionals working in mental health or the disability field, family members, and other stakeholders relevant to the context in which the training is provided. People with psychosocial disabilities and their organizations are central actors in the intervention: They are not only passive recipients but are involved as leaders in all the phases of the training organization and delivery. Another innovative element of the QualityRights training is that people with psychosocial disabilities were actively involved in all the phases of its development, while in the past, such initiatives have reflected only the perspective of mental health professionals.

Currently, there is a growing interest in the QualityRights training, and the WHO is implementing it in different countries [58, 173, 174]. However, the efficacy of this intervention has not been rigorously evaluated. We have seen that the results of studies conducted in the past (and evaluating interventions with kindred objectives) may be biased due to confounding, selection bias, and information bias issues. To avoid these limitations, when evaluating the efficacy of the QualityRights training, I propose to carry out a Randomized Controlled Trial targeting mental health professionals. The use of random assignment to the intervention would help guarantee exchangeability in expectation (at least, at the beginning of the study). Differently from the past, the impact of attrition and non-adherence to the assigned intervention throughout the study should be assessed. Since previous studies usually provided only data on pre-post intervention evaluations, the trial I propose should follow up participants for at least three months, with multiple measures over time (pre-intervention, post-intervention, at three months). A better definition of the outcomes, as well as the use of measures tested for reliability and validity, would also be necessary. Since the assessment of behavioral changes has been neglected in prior research, particular

attention would be given to this area.

Given the impact human rights violations have on the health of people with psychosocial disabilities, an effort is needed to carry out methodologically strong research that will provide robust evidence to support further investment in interventions such as the QualityRights training and make steps forward promoting the rights of people with psychosocial disabilities.

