Furthermore, all the studies evaluating the efficacy of these different interventions present critical methodological limitations. Many were pre-post intervention studies without a control group. Even when the control group was present, most of the studies were non-randomized, and thus we cannot exclude non-comparability between the intervention and the control group. In the rare cases where a randomized controlled trial was carried out, the samples enrolled were too small to draw definitive conclusions, and no power calculations were provided. Response rates in many pre-post intervention studies were low, particularly in the post-intervention assessments, and this may have caused selection biases. Information bias was an issue in many studies since the changes in knowledge and in attitudes were often evaluated with questionnaires not tested for reliability and validity. No attempt to quantify the impact of these biases was made in any of these studies. Furthermore, although the number of publications on interventions to promote people with psychosocial disabilities' rights (in the mental health sector and more broadly) is growing, no recent attempt has been made to systematically review the literature on this topic to inform future research and interventions.

Justifying a cluster randomized controlled trial (cRCT) to test a new intervention, the WHO QualityRights training

Recently, the World Health Organization (WHO) has developed the QualityRights (QR) training. This training is different from those previously implemented because it applies the modern human rights framework of the UN CRPD and is designed to have people with psychosocial disabilities as central actors in all the activities. People with psychosocial disabilities and their organizations were also actively involved in all the phases of the WHO QR development. The WHO QR intervention includes modules to increase knowledge about the rights of people with psychosocial disabilities and change the negative attitudes towards them and their role as rights holders. Furthermore, the training provides mental health providers with the skills necessary to advocate for a human rights-based approach in mental health and support people with psychosocial disabilities to advocate for their own rights.

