Currently, there is a growing interest in the QualityRights training, and the WHO is implementing it in different countries [58]. However, the efficacy of this intervention has not been rigorously evaluated. We have seen that the results of studies conducted in the past (and evaluating interventions with similar objectives) may have been biased due to confounding, selection bias, and information bias issues. To avoid these limitations, when evaluating the efficacy of the WHO QR training, I propose to carry out a cRCT targeting mental health professionals. The use of random assignment to the intervention would help guarantee exchangeability in expectation (at least, at the beginning of the study). The impact of biases due to attrition and non-adherence to the assigned intervention throughout the study should be assessed. A better definition of the outcomes, as well as the use of measures tested for reliability and validity, would also be necessary.

The cRCT I propose will be carried out in Ghana. In Ghana, inhumane practices and violations of persons with psychosocial disabilities' rights are common, as documented by local NGOs and international organizations [59]. In 2012, Ghana enacted a Mental Health Act [60] intended to eliminate the widespread abuses against people with psychosocial disabilities in mental health services and the general community. However, eight years later, violence and abuses against people with psychosocial disabilities are still frequent in the country [9]. To address this situation, the Mental Health Authority of Ghana (Ministry of Health), in partnership with local organizations of people with psychosocial disabilities, expressed an interest in implementing the WHO QualityRights training and are willing to support the conduct of the cRCT here proposed in their country.

Specific aims

To conduct a cRCT in Ghana to determine the efficacy of the QualityRights training compared with a placebo intervention in improving the knowledge about human rights and the attitudes of mental health professionals towards people with psychosocial disabilities and their role as right-holders.

Secondarily, we want also to determine

- if the QualityRights training, compared with a placebo intervention, is effective in changing the practices and experiences related to substitute-decision making and coercion among mental health providers.

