The trial's primary hypothesis is that mental health professionals who receive the WHO QualityRights intervention will have a better knowledge about human rights and improved attitudes towards people with psychosocial disabilities and their role as right-holders, compared with their colleagues who receive the placebo intervention. Furthermore, mental health professionals who receive the WHO QualityRights training will resort less to practices related to substitute-decision making and coercion compared with their colleagues who receive the placebo intervention.

2. Significance

2.1 Violations of the human rights of persons with psychosocial disabilities: Dimension of the problem.

People with psychosocial disabilities are commonly exposed to human rights violations both within the mental health care system and in the general community [1-5]. Such violations occur in all countries, although most of the academic research in this field has been carried out in high-income countries [2, 4]. In middle- and low-income countries, our knowledge about this issue is more fragmentary and comes mainly from the media and reports from human rights and other non-governmental organizations [2]. To provide an idea of the gravity and pervasiveness of the problem, I will present an overview of the most common human rights violations against people with psychosocial disabilities: a) discrimination and exclusion from society; b) inability to access adequate mental health services; c) physical, sexual, and psychological abuse, violence, and neglect; and d) denial of the right to legal capacity [2, 4].

(a) Discrimination and exclusion from society.

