3.2.1.10. Collection of data and Assessment instruments

All the data will be collected through an online platform and made confidential according to the provisions that protect privacy in Europe (Articles 6 and 9 of EU Regulation No. 679) and Ghana (Data Protection Act, 2012).

- The **sociodemographic questionnaire** will include the following information:
 - I. Gender;
 - II. Age in years;
 - III. Educational attainment;
 - IV. Marital status;
 - V. Number of children;
 - VI. Religion;
 - VII. Profession;
 - VIII. Years working in a mental health service;
 - IX. Hospital and unit of work;
 - X. Region of residence;
 - XI. Main language;
 - XII. Family member(s) with a psychosocial disability;
 - XIII. Identification as “person with a psychosocial disability”.

In the case the WHO QualityRights intervention will be found to be not effective, these sociodemographic variables may be used to understand for which subgroups or under what circumstances the training did not work (although this work is outside the scope of the present proposal).

Primary outcomes

- The **World Health Organization’s Knowledge about the Rights of persons with psychosocial disabilities questionnaire** [Appendix 6] (16 items) was developed by WHO to assess knowledge about

the rights included in the UN CRPD. People with psychosocial disabilities had an active role in all the phases of the scale development.

- The **World Health Organization's questionnaire on the attitudes towards people with psychosocial disabilities as rights-holders** [Appendix 7] (17 items) was developed by WHO and includes three subscales: attitudes towards institutionalization and living independently in the community; attitudes toward mandatory treatment and coercion; attitudes toward people with psychosocial disabilities as decision-makers. People with psychosocial disabilities had an active role in all the phases of the scale development.

Secondary outcomes

- The **Practices related to substitute-decision making and coercion scale** [Appendix 8] (12 items) is a scale developed to measure the use of substitute-decision making and coercive practices in mental health units.

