3.2.1.11 Blinding

Given the nature of the intervention, participants will not be blinded to their intervention arm. However, participants will not be informed of the study hypotheses and will know to which intervention arm they are assigned only after completing the pre-intervention assessment. Data analysts will have access only to anonymized data at the end of each assessment phase. Data will be presented for Group 1 and 2 without the data analysts knowing what 1 and 2 refer to in terms of intervention and control arms.

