5	Free from coercion, violence, and abuse	This module provides information on how and why violence, coercion, and abuse occur in mental health settings and the general community. During this workshop, participants learn about the negative impact these practices have on people with psychosocial disabilities and examine the role of power relations in exacerbating violence, coercion, and abuses. Furthermore, participants learn about key strategies and approaches which have been shown to be effective in ending human rights violations within mental health services.

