Appendix 8. The Practices related to substitute-decision making and coercion questionnaire.

Please indicate how many times in the last month you used the following strategies **within your psychiatric unit**.

Select only one option for each statement.

		Every day	A few times a week	Once a week	A few times a month	Once a month or less	A few times in the last three months	Never
1	I used seclusion (for instance, ordering or keeping service users in a locked room)							
2	I used physical restraints (for instance, using ties or other mechanical devices to restrain service users)							
3	I prescribed or administered a treatment although the service user did not want it							
4	I supported service users to write their recovery plan							
5	I informed service users about their rights (including their right to refuse treatment)							
6	I used chemical restraints (for instance, prescribing or administering an injection to calm the behavior of service users without their consent)							
7	I yelled or used verbal aggression to get service users to comply with requests							

For each statement, mark the box that most accurately reflects your response.

		A lot less than me	Less than me	As much as me	More than me	A lot more than me
8	Mental health professionals in my unit use seclusion and physical/chemical restraints					
9	Mental health professionals in my unit yell or use verbal aggression to get service users to comply with requests					
10	Mental health professionals in my unit prescribe or administer treatments to control the behavior of service users					
11	Mental health professionals in my unit respect the will and preferences of service users					
12	Mental health professionals in my unit use restraints to control unsettled situations in the ward					

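### The secondary aim and hypothesis speak of conduct, but the only measure is a questionnaire answered by unblinded staff, so the claim should be limited to self-reported practices

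*Protocol*

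**What the plan says.** **The claim.** Section 1 (Specific aims), repeated in section 3.1, makes a change in practices related to substitute decision-making and coercion a secondary aim. The hypothesis paragraph that follows the aims says that staff who receive the training "will resort less to practices related to substitute-decision making and coercion compared with their colleagues who receive the placebo intervention".

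**The measure.** Section 3.2.1.10 lists one instrument for practices, which "is a scale developed to measure the use of substitute-decision making and coercive practices in mental health units". Appendix 8 shows its form. Items 1 to 7 open with "Please indicate how many times in the last month you used the following strategies" and ask for the respondent's own frequency of use. Items 8 to 12 ask how far other professionals in the same unit do such things, on a five-point scale anchored on the respondent. All data come through an online platform. Appendix 5 schedules the scale at baseline, 3 months and 6 months.

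**The respondents.** Section 3.2.1.11 says: "Given the nature of the intervention, participants will not be blinded to their intervention arm". Arm is disclosed only after the baseline assessment, the study hypotheses are withheld, and the analysts are masked.

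**The training.** In Appendix 2, Module 4 covers the ban on substitute decision-making and coercion. In Module 5 "participants learn about the negative impact these practices have on people with psychosocial disabilities". The control arm takes a COVID-19 course (Appendix 4) with no such content.

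**The analysis.** Section 3.1.2.4 evaluates change in practices with the method used for the primary outcomes.

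**The concern.** The hypothesis is about behaviour and the data are about reported behaviour. In many trials that gap is harmless, because any misreporting is similar in both arms. Here the assigned course may itself change how the questions are answered: one arm has just been taught that the listed acts are prohibited and damaging, and the other has not. Randomising units does not balance a reporting shift that the intervention causes.

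Section 1 calls a change in practices the ultimate goal, and section 2.6 says the Ghanaian authorities want the training evaluated before it is scaled up nationally. A difference on this scale, read through the hypothesis as worded, would be taken as less coercion on the wards when the data cannot show that.

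**Working it through.** **1. Is any item independent of the trained, unblinded respondent?**
- Items 1 to 7 are first-person reports.
- Items 8 to 12 concern colleagues, but the same respondent answers them. The colleagues work in the same unit and so in the same arm, and the rating is relative to the respondent's own use.
- The other secondary instrument, the abbreviated SREQ, records experiences and opinions of the same staff.
- Section 3.2.1.10 and Appendix 5 list no seclusion or restraint register, observer or service-user report.

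So no item is an independent source.

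**2. Which way would a reporting shift go?**
- Items 1 to 7: the likely shift in the trained arm is to understate coercive acts and overstate the supportive ones (items 4 and 5). Both favour the training.
- Items 8 to 12: a respondent who understates personal use may rate colleagues as using coercion more than they do (items 8, 9, 10, 12) and as respecting preferences less (item 11). These answers move against the training.
- Appendix 8 gives no scoring rule, so the net direction on the 12-item total cannot be derived.

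**3. How large could the effect be?** The documents give no size for the shift, so a range is assumed.

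Inputs (section 3.2.1.14): 126 per arm, 28 units allocated 1:1 (14 per arm), 20% loss, ICC 0.05, two-sided alpha 0.05. These were set for the attitudes questionnaire and are borrowed here.

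The plan's own figure first. The protocol does not state its formula, but one route reproduces 126. A t test with 2 × (14 − 1) = 26 df at 0.5 SD and 80% power needs 85 analysed per arm. That is 85 / 14 = 6.07, so 7 per unit; 7 / 0.8 = 8.75, so 9 per unit; 9 × 14 = 126.

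Standard error of a between-arm difference at one visit:
- Analysed per arm: 126 × 0.8 = 100.8
- Per unit: 100.8 / 14 = 7.2
- Design effect: 1 + (7.2 − 1) × 0.05 = 1.31
- SE = √(2 × 1.31 / 100.8) = 0.161 SD

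Probability of a significant difference with no true change and an assumed net shift b (noncentral t, 26 df, noncentrality b / 0.161):

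| b (SD) | Two-sided total | In the direction of the shift |
|---|---|---|
| 0 | 5.0% | 2.5% |
| 0.1 | 9.2% | 8.7% |
| 0.2 | 22.3% | 22.2% |
| 0.3 | 43.3% | 43.3% |

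With the ICC varied from 0.10 to 0.01, the two-sided total is 19% to 26% at 0.2 SD and 36% to 51% at 0.3 SD. The calculation is symmetric: a net shift against the training would give a spurious adverse result equally often.

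**The case against.** **Safeguards exist.** The protocol withholds the hypotheses, discloses the arm only after baseline, collects data confidentially online and masks the analysts. These count for something. But disclosure after baseline and masked analysis do not affect answers given at 3 and 6 months, and the course content itself signals the preferred answer even when the hypotheses are withheld.

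**Own conduct only, and biased towards the training.** A reader might infer that the hypothesis rests solely on staff describing their own acts, and that the bias must favour the training. The documents do not support either. Five of the 12 items concern colleagues, and their anchoring on the respondent can pull the total the other way. Module 5 also teaches how and why coercion arises, which could make staff recognise and report more of it.

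**Self-contradiction.** A reader might infer that the protocol breaks its own standard, since it says of earlier studies "No attempt to quantify the impact of these biases was made in any of these studies" and then "To avoid these limitations, when evaluating the efficacy of the WHO QR training, I propose to carry out a cRCT targeting mental health professionals". That goes too far. The information bias complained of there comes from questionnaires not tested for reliability and validity, in studies of knowledge and attitudes. The biases that section 1 says should be assessed in this trial are attrition and non-adherence. Section 3.2.1.10 sends the psychometric evaluation of this scale to a separate document.

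**A missing sensitivity analysis.** A reader might also count its absence from section 3.1.2.4 as a defect. Such analyses commonly sit in the SAP, which is not at hand. A tipping-point analysis would add nothing in any case: moving the estimate by a constant until the 95% interval includes zero only returns the confidence limit nearest zero, and section 3.1.2.3 already promises 95% intervals.

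**Generic arithmetic.** The percentages would follow for any self-reported outcome with the same inputs and assumed shift. That is fair, and they are offered as scale only. The protocol also sets no rule for what will be concluded, so it cannot be said that it commits to a false claim.

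**Conclusion.** The point holds as a limit on what the secondary outcome can support. The aim and hypothesis state conduct; the instrument records what unblinded staff report, in a trial where one arm alone is taught that the acts are banned and harmful. A difference on the scale cannot tell less coercion from changed reporting of it.

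The direction is likely favourable to the training on items 1 to 7 and undetermined on the total. The size is unknown. The figures of about 9%, 22% and 43% rest on an assumed net shift of 0.1, 0.2 or 0.3 SD, on an ICC and sample size set for attitudes, and on a single-visit comparison instead of the planned longitudinal model. The primary outcomes are outside this point.

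**What to change.** - In the secondary aim (section 1, Specific aims, and section 3.1), the hypothesis paragraph and section 3.1.2.4, replace practices with self-reported practices.
- In section 3.1.2.4, add one sentence: a between-arm difference on the Appendix 8 scale alone will not be reported as a reduction in coercion.

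No new data, visits or analyses are needed, and no tipping-point analysis is asked for. The cost is a few words and a less favourable secondary claim. A claim about conduct itself would need a source outside the participants' own answers, which the protocol does not plan.
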